Record Date of Last Menses ¹¹	X	X	X	X	X	X	X	X	X	X	X
Pregnancy Test ¹²	X	X	X	X	X	X	X	X	X	X	
Serum Hormone Evaluation ¹³	X	As clinically indicated								As clinically indicated	As clinically indicated
Steady-state and post-treatment pharmacokinetic collection of blood (AT SELECTED SITES ONLY) ²⁴		One collection while taking vismodegib for at least 2 weeks continuously									At 3, 6, 9, and 12 Months ONLY
QoL Assessments using Skindex-16 (in selected sites)	X		X					X		X	

Table 1 Schedule of Assessments (cont.)

Cycle	Screening / Baseline	Treatment Phase ¹ (Allowed Visit Window +/- 3 days from Cycle 2 onwards)								End of Treatment Visit ²	Safety Follow-Up Visits ³ (1 month, 3 months, 6 months, 9 months, 12 months after the last dose of vismodegib (GDC-0499))
		1	2	3	4	5	6	7	8 onwards		
Day	-28 to -1	1	29	57	85	113	141	169	Every 28 Days		
Symptom Assessment using MDASI ¹⁴	X	X	X	X	X	X	X	X	X	X	X
Tumor Assessments (physical examination) ^{15, 17}	X	Every 4 to 8 weeks from the time of the first dose (±5 days) regardless of dosing delays.								X	
Tumor Assessments (by imaging techniques, if required) ^{16, 17}	X	Every 8 to 16 weeks from the time of the first dose (±5 days) regardless of dosing delays or as per institutional standards In metastatic BCC patients (newly enrolled after approval of the Study Protocol, version 4.0), every 8 weeks from time of first dose (±5 days) regardless of dosing delay								X	
AEs / SAEs ¹⁸	X	X								X	X
AE-related pharmacokinetic collection of blood (AT SELECTED SITES ONLY) ²⁵											At 6, 9, and 12 Months ONLY
Ultrasound ¹⁹	X	As clinically indicated								As clinically indicated	As clinically indicated
Follow-up for disease progression		X								X	X
Tumor biopsy and collection of whole blood ²⁰										X	
Concomitant medication	X ²¹	X								X	X
New anti-cancer therapy										X	X
Drug Dispensing		X (first day of each Cycle)									
Drug Accountability ²² Drug Dosing Exception Diary ²³			X	X	X	X	X	X	X	X	X

Table 1 Schedule of Assessments (cont.)

Notes Results of screening tests or examination performed as standard of care before obtaining informed consent and within the specified interval may be used rather than repeating required evaluation. Day 1 = first dose of study drug vismodegib.

1. Visits during the treatment period are to be completed on Day 1 of every 28-Day Cycle.
2. End of Treatment Visit will be performed when the patient discontinues vismodegib regardless of when it occurs.

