5.3.2 Treatment Phase Assessments

Day 1 of the study will be defined as the first day a patient receives vismodegib. One cycle of therapy is defined as 28 days of treatment. During the Treatment Phase, all study assessments will be conducted on Day 1 (± 3 days) of each Cycle, with the exception of tumor evaluation, for which a window of ± 5 days will apply (see below).

The assessments during the treatment period are:

- Limited physical examination at every 28-day visit
- Vital signs (body temperature, blood pressure, and pulse) and weight at every 28-day visit
- ECOG PS assessment at every 28-day visit
- Hematology (including hemoglobin, hematocrit, red blood cell count, full white blood cell count including differential, platelet count, and ANC) at every 28-day visit
- Biochemistry (including glucose, sodium, potassium, chloride, bicarbonate, blood urea nitrogen, creatinine, creatine kinase [also known as creatine phosphokinase], total bilirubin, alkaline phosphatase, AST, and ALT) at every 28-day visit
- Urine pregnancy tests on Day 1 of each subsequent Cycle. If a urine pregnancy test is positive, it must be confirmed by a serum pregnancy test
- 12-lead ECG (during the study if clinically indicated)
- Concomitant therapy and AEs (including SAEs) throughout the study
- For women of childbearing potential:
 - Record date of last menses
 - Ultrasound (as clinically indicated [see Schedule of Assessments])
 - Assess amenorrhea/irregular menses that develops while on study:
 1. At start of amenorrhea/irregular menses, perform serum hormone evaluation at study site, including FSH, LH, E2, and TSH, and refer to gynecologist or appropriate specialist for assessment of ovaries and uterus, including ultrasound
 2. At resolution of amenorrhea/irregular menses, perform serum hormone evaluation at site, including FSH, LH, E2, and TSH. Refer to gynecologist or appropriate specialist for follow-up ultrasound ONLY if there was abnormality identified during previous ultrasound
 3. If amenorrhea/irregular menses recurs, repeat evaluations at start of recurrence as detailed previously
- Vismodegib administration throughout the study
- Tumor assessment (the majority of the patients in this study have locally advanced BCC and in this disease setting measurable tumors are accessible to evaluation by physical examination). Objective responses using RECIST, v1.1 should be confirmed by repeat assessments at least 4 weeks after initial documentation of response:

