## **Definition of First Dose**

Earliest date of drug dispensed when the amount of drug taken is greater than 0 and the doses are not missed on this date, in case the dose is missed on this date then take the date of the day after the last dose missed amongst the first group of missed doses. A drug is considered 'taken' if there is a non-zero, non-missing 'Taken' record in the subject's Drug Accountability CRF page.

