## **Reference Date (Study Day 1)**

Where derivations refer to reference date please use date of first dose as there is no randomization date available.

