## **Baseline**

Baseline is considered as the most recent time prior to treatment. If a record is collected on the day of first dose, then that record is considered as baseline.

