## Output Specifications: Safety Outputs

### Exposure:

Capsules are dispensed to each subject at the time of each visit and are recorded on the CRF. Subjects take a dose of 150 mg daily and fill in any missed dose dates on the Patient Diary, in case of dose missed for any reason. The investigator completes the number of capsules taken between visits on the basis of number of capsules returned by the subject at the next visit.

It is possible for a subject to have taken all the dispensed capsules between two visits and still have a missed dose if there is a delay in scheduling or attending the next visit. Consider the total number of capsules dispensed, taken, and the missed dosing date for daily dose calculation (ie, consider the sum of all dispensed/taken doses).

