## Adverse Events:

### General AE Reporting

Listings will include all AEs unless otherwise specified. A Treatment Emergent AE (TEAE) is defined as an AE that starts on or after the first day of study treatment and within 30 days of last dose (please see General Considerations for definition). Unless otherwise specified, AE and SAE summary tables will be restricted to TEAEs.

In STEVIE, the data collection guidelines require that the same AE is entered multiple times into the database, with a separate record for each change in toxicity grade or Lower Level Term. AEs can be reported using this or a “collapsed” Adverse Events analysis dataset.

The Collapsed Adverse Events dataset is derived by combining records that can be reasonably considered to be referring to a single AE term but with changes in toxicity grade (or lower level term). Records from the original AE dataset are grouped, and each group is represented in the collapsed dataset by a single record. The groups are built up by “chaining” records from the original dataset as follows:

- if the Subject ID, System Organ Class and Preferred Term are the same, and
- either the periods defined by the two AEs’ start and end dates overlap, or the Start Date of the later AE is  $\leq 2$  days after the End Date of the earlier one.

In the single record representing the “collapsed” AE:

- Subject ID, System Organ Class and Preferred Term are copied across from any of the records in the group (these are identical so it doesn’t matter which record these variables come from)
- Severity (i.e. toxicity grade) is taken as the most severe grade in the group
- Start Date is taken as the earliest start date in the group
- End Date, Lower Level Term and Outcome are taken from the record with the latest end date in the group

Examples are given on the next page.

Example of derivation of “collapsed” AEs:

Example 1:

SUBJID	System Organ Class	Preferred Term	Lower Level Term	Severity	Outcome	Start Date	End Date
	GASTROINTESTINAL DISORDERS	DYSPEPSI	DYSPEPSIA	GRADE 2 / MODERATE	RESOLVED		
	GASTROINTESTINAL DISORDERS	DYSPEPSI A	HEART BURN	GRADE 3 / SEVERE	RESOLVED		

Collapsed to:

	GASTROINTESTINAL DISORDERS	DYSPEPSI A	HEART BURN	GRADE 3 / SEVERE	RESOLVED		
--	----------------------------	------------	------------	------------------	----------	--	--

Example 2:

SUBJID	System Organ Class	Preferred Term	Lower Level Term	Severity	Outcome	Start Date	End Date

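### A blank Cycle 1 capsule count is treated as no dose, which moves derived Study Day 1 to about Day 29 and takes first-cycle adverse events out of the summary tables for the patients affected

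*SAP*

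**What the plan says.** SAP, Definition of First Dose, takes the "Earliest date of drug dispensed when the amount of drug taken is greater than 0 and the doses are not missed on this date". If that day was missed, the date moves to the day after the first run of missed doses. The section counts drug as taken only "if there is a non-zero, non-missing 'Taken' record in the subject's Drug Accountability CRF page". Under SAP, Exposure, the investigator fills in the number taken "on the basis of number of capsules returned by the subject at the next visit".

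Several derivations hang on this date:

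- **Study Day 1.** Under Reference Date, derivations should "please use date of first dose as there is no randomization date available".
- **Baseline.** "Baseline is considered as the most recent time prior to treatment", and a record collected on the day of first dose also counts as baseline.
- **Treatment emergence.** Under General AE Reporting, an event qualifies if it "starts on or after the first day of study treatment and within 30 days of last dose". The definition is referred back to General Considerations. AE and SAE summary tables are limited to these events unless stated otherwise, while listings keep all events.
- **Efficacy.** Time to response, PFS and OS all run from first treatment.

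The SAP's Safety and Intent-to-Treat populations each need only one capsule count that is neither zero nor missing, at any cycle.

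Protocol 5.3.2 says that "Day 1 of the study will be defined as the first day a patient receives vismodegib". Protocol Table 1 has drug dispensed on the first day of each cycle, and its note 1 reads "Visits during the treatment period are to be completed on Day 1 of every 28-Day Cycle".

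**The concern.** The rule treats not knowing how many capsules were taken as knowing that none were. A patient whose Cycle 1 count is blank but whose later counts are recorded stays in the safety and ITT sets, because one later count is enough. The clock for that patient starts at the second dispensing. The SAP text gives no fallback, such as the Cycle 1 visit date. The patient diary cannot supply one, since it records only missed doses (Protocol Table 1, note 23).

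Safety is the primary objective and the AE summary tables are its main output. For affected patients the error works in one direction: events that began in the first four weeks on drug are classed as pre-treatment. Changes from baseline are also affected, because a Day 29 laboratory value, weight, ECOG grade or Skindex-16 score (the questionnaire is due after Cycle 1) would fall on the derived first-dose day and so serve as baseline.

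**Working it through.** **1. The plan's own figure.** Visit day = 1 + 28 × (cycle − 1). Cycles 1 to 7 give Days 1, 29, 57, 85, 113, 141 and 169, matching Protocol Table 1. The second dispensing is therefore Day 29, or Day 26 to 32 with the ±3-day window that applies from Cycle 2.

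**2. Applying the first-dose rule** (earliest dispensing whose count is neither missing nor zero) to a patient dispensed drug in six cycles:

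| Cycle 1 count | Later counts | Derived first dose |
|---|---|---|
| Recorded, above zero | Recorded | Day 1 |
| Blank | Recorded | Day 29 (26 to 32) |
| Entered as all 32 capsules taken | Recorded | Day 1 |
| Blank, only Cycle 1 dispensed | None | No date; outside the safety and ITT sets |

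**3. Size of the shift per affected patient.** 29 − 1 = 28 days (25 to 31). Using the SAP's divisor for months, 28/30.4375 = 0.92 month (25/30.4375 = 0.82; 31/30.4375 = 1.02). PFS, OS, time to response and treatment duration each shorten by that amount.

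**4. Which events leave the tables.** With first dose at Day 29, onsets on true Days 1 to 28 precede it. In the uncollapsed dataset each grade change is a separate record, so a change on or after Day 29 can still count the patient. In the collapsed dataset the earliest start date is kept, so an event that began in Cycle 1 drops out whole, however long it lasted.

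**5. A knock-on in best response.** The SAP requires an assessment at least 51 days after first dose for stable disease. A Day 57 assessment is 57 − 1 = 56 days from the true start but 57 − 29 = 28 days from the derived one, so it no longer qualifies. A patient whose only qualifying assessment is that one, and who then progresses, would be coded as progressive disease. The response rate itself is not changed by this.

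**6. Effect on reported incidence.** The documents give no rate of blank Cycle 1 counts, so both inputs here are assumptions: m is the share of patients affected, and f is the share of patients with the event who have it only in Cycle 1. Reported incidence = true incidence × (1 − m × f), with 1200 patients planned.

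| m | f | True 10% reported as | True 68% reported as |
|---|---|---|---|
| 1% (12 patients) | 10% | 9.99% | 67.93% |
| 5% (60 patients) | 50% | 9.75% | 66.30% |
| 10% (120 patients) | 50% | 9.50% | 64.60% |

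The 68% is the muscle-spasm incidence that the protocol reports from the earlier pivotal study. In the middle row at 10%, 1200 × 0.05 × 0.10 × 0.50 = 3 patients are lost from 120, and 117/1200 = 9.75%.

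**The case against.** **The trigger is inferred.** A reader might conclude that any unreturned Cycle 1 bottle moves Day 1. The documents do not support that. They say the count is worked out from returned capsules but not what a site enters when nothing comes back. If the site records every capsule as taken, nothing shifts. This objection stands: the defect is tied to a blank field, and an unreturned bottle is only one possible route to it. The SAP does allow for missing counts in its own definitions.

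**Controls exist.** Accountability is done at each visit from Cycle 2, sites keep dispensing and return logs, and validation checks and monitors look for incomplete forms. These should make a lasting blank uncommon. They do not change what the rule does with one.

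**The effect is small.** At the middle assumption in the table, a 10% incidence moves by 0.25 percentage point, against a stated precision of 1.6 to 1.8 points. This also stands as to size. It is a bias, though, and the confidence interval does not account for it.

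**Survival endpoints.** It is tempting to set 0.92 month against the pivotal study's 9.5-month median PFS and call it a 10% loss. That compares one patient's shift with a cohort median. If 1% to 5% of patients were affected, the average shift would be 0.92 × 0.01 to 0.92 × 0.05, or 0.009 to 0.046 month.

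**Conflict with the protocol.** The SAP rule gives the protocol's Day 1 whenever the Cycle 1 count is present and above zero. The two part only when that count is blank.

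**Material not seen.** The DAP M3, which the SAP cites for visit windows, the data cut and other derivations, was not available. The SAP does not send the reader there for first dose, but a fallback in it cannot be ruled out.

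**Conclusion.** The concern holds in a limited form. The first-dose rule equates a missing Cycle 1 count with zero and, where a later count exists, returns a date 25 to 31 days too late for a patient who did start in Cycle 1. For those patients, first-cycle events leave the summary tables, baseline can be an on-drug value, and times measured from first dose shorten by about 0.92 month.

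It would go too far to say that first-cycle events are lost from the report, because listings keep all of them and some return through later grade-change records. The documents also do not show that the trial's main results are materially distorted: the number of affected patients is not given, and the effect on overall incidence is probably small unless blanks are common. The change is still worth making because this is a stated rule that yields a wrong date, it biases the primary safety output towards fewer early events, and it is cheap to correct. The conclusion assumes that some Cycle 1 counts are left blank and that no fallback exists outside the SAP.

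**What to change.** - **Definition of First Dose.** Use the first dispensing date, with the existing missed-dose adjustment, unless the Cycle 1 count is recorded as zero. A missing count is then treated as dosed.
- **Safety and Intent-to-Treat populations.** Handle missing counts the same way. Otherwise a patient who was dispensed drug but has only blank counts would have a first-dose date and yet sit outside both sets.
- **Check listing.** List every patient whose first dose by capsule count falls more than 3 days after first dispensing, and resolve each before database lock. The listing also shows how often the problem occurs; if it is empty, no date was shifted by more than that margin.

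The cost is one changed derivation, two aligned population definitions, one listing and a rerun of existing outputs; the SAP already shows tables from the 3 August 2015 snapshot. The downside is that a rare patient who took nothing from an uncounted bottle would be given too early a start, or be included in the safety and ITT sets when not dosed.

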## **Definition of Last Dose**

Latest date of drug returned where amount taken is greater than 0 and the doses are not missed on this date, in case the dose is missed on this date then take the date of the day before the first dose missed amongst the last group of missed doses.

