18. AEs will be collected on Day 1 of each Cycle and at the follow-up or early termination visit. After informed consent, but prior to initiation of study medications, only SAEs caused by a protocol-mandated intervention will be collected. All AEs (either related to study specific procedures or otherwise) experienced after the patient has signed the Informed Consent form but before they have received study treatment, should be recorded as medical history. All AEs experienced after the patient has started study treatment must be recorded on the AE form of the eCRF, as well as all new AEs experienced during the study and up to 1 month, 3 months, 6 months, 9 months, 12 months after the last dose of study treatment (\pm 5 days). Additionally, non-serious, new AEs considered related to study drug which occur approximately (\pm 5 days) 1 month, 3 months, 6 months, 9 months, 12 months after the last dose of study drug should also be reported. SAEs considered related to study drug should be reported indefinitely.
19. In women of childbearing potential ONLY. At start of amenorrhea/irregular menses, refer to gynecologist or appropriate specialist for assessment of ovaries and uterus, including ultrasound. At resolution of amenorrhea/irregular menses, refer to gynecologist or appropriate specialist for follow-up ultrasound ONLY if there was abnormality identified during previous ultrasound. If amenorrhea/irregular menses recurs, repeat evaluations at start of recurrence as detailed previously. Obtain copy of results from ultrasound and enter any abnormal findings into the CRF.
20. In metastatic BCC patients who develop tumor progression on vismodegib treatment, a biopsy will be performed if at least one of the progressing lesions is accessible, e.g., skin, superficial mass, or lymph node and a whole blood sample will be collected.
21. All concomitant medications used within 14 days before study treatment and up to the end of treatment and approximately (\pm 5 days) 1 month, 3 months, 6 months, 9 months, and 12 months after the last dose of vismodegib at the Safety Follow-Up Visit must be recorded.
22. Study drug vismodegib accountability will be performed at every study visit from Cycle 2 onwards and at the End of Treatment Visit.
23. Patients will keep a diary to record ONLY those occasions when a vismodegib dose was missed. The patient will bring this diary with him/her to each study visit to allow missed doses to be recorded by the Investigator.

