### 4. Listing of Primary Reason for Patients Prematurely Discontinuing Treatment

Disease Status: Locally Advanced

Center/ Patient ID	Age/Sex/Race	Date of First Study Drug Administration	Day of Last Study Drug Administration	Day of Treatment Discontinuation	Reason for Treatment Discontinuation	Other Reason for Treatment Discontinuation
xxxxxx/xxx	x	xxxx-xx-xx	xxx	xxx	ADVERSE EVENT	
xxxxxx/xxx	x	xxxx-xx-xx	xx	xx	ADVERSE EVENT	
xxxxxx/xxx	x	xxxx-xx-xx	xxx	xxx	PROGRESSIVE DISEASE	
xxxxxx/xxx	x	xxxx-xx-xx	xx	xx	ADVERSE EVENT	
xxxxxx/xxx	x	xxxx-xx-xx	xx	xx	ADVERSE EVENT	
xxxxxx/xxx	x	xxxx-xx-xx	xxx	xxx	ADVERSE EVENT	
xxxxxx/xxx	x	xxxx-xx-xx	xxx	xxx	PROGRESSIVE DISEASE	
xxxxxx/xxx	x	xxxx-xx-xx	xxxx	xxxx	WITHDRAWAL BY SUBJECT	
xxxxxx/xxx	x	xxxx-xx-xx	xxx	xxx	ADVERSE EVENT	
xxxxxx/xxx	x	xxxx-xx-xx	xxx	xxx	OTHER	'Patient requested to discontinue treatment but agreed to continue in follow up'

Programming note:

- Include safety evaluable patients who discontinued from study drug treatment.
- Variables to include: Centre, Subject, Age, Sex, Race, Date of Treatment Start, Day of Last Treatment, Study Day of Treatment Discontinuation, Reason and Other Reason for Treatment Discontinuation.
- Please see programming notes for the l\_ds\* output.
- Please see information for the output ID: DSL02.

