#### Programming Note:

- The number of days of missed dose (and so the number of missed doses) will be calculated as follows: The number of days between the first and last dose, minus the sum of the number of capsules taken according to the Dose Accountability CRF page. i.e. If first dose was the 1st Jan, and the last dose

as the 28th Feb, and the subject had taken 55 capsules (according to their 'taken' records, then there would be 4 (59-55) missed doses.

- Cumulative dose of Vismodegib will be calculated as the sum of the total number of capsules taken (recorded on the Dose Accountability CRF page) at each visit multiplied by 150 mg.
- Duration on treatment will be calculated as time from first dose date to last dose date (last dose date minus first dose date + 1), measured in days.
- Dose intensity will be calculated as the sum of the total number of capsules taken (recorded on the Dose Accountability CRF page) at each visit / sum of the total number of capsules dispensed (recorded on the Dose Accountability CRF page) at each visit x 100.

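### Last dose is taken from the drug-return date without a check against the recorded discontinuation date, so undocumented days after stopping can count as treatment time and as missed doses

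*SAP*

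**What the plan says.** **Last dose.** SAP, General Considerations, Definition of Last Dose, has two parts. The main rule is "Latest date of drug returned where amount taken is greater than 0", provided that no dose was missed on that date. The fallback is "in case the dose is missed on this date then take the date of the day before the first dose missed", where the first missed dose is that of the final group of missed doses.

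**Where missed-dose dates come from.** SAP, Exposure, says patients take one dose daily and "fill in any missed dose dates on the Patient Diary". Protocol Table 1, note 23, says "Patients will keep a diary to record ONLY those occasions when a vismodegib dose was missed".

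**When drug comes back.** Protocol Table 1, note 22, says "accountability will be performed at every study visit from Cycle 2 onwards and at the End of Treatment Visit". Protocol 5.3.3 places the End of Treatment Visit at the point where the patient discontinues vismodegib.

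**The discontinuation date.** The SAP uses a CRF discontinuation date to define the Potentially Reversible AE population. Its Disposition section cites an End of Study Treatment page. The listing of reasons for premature discontinuation shows, side by side, "Day of Last Treatment, Study Day of Treatment Discontinuation, Reason and Other Reason for Treatment Discontinuation". No rule reconciles the two dates.

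**What depends on last dose.** In the Programming Note to the overall exposure table, "Duration on treatment will be calculated as time from first dose date to last dose date", and missed doses are days minus capsules taken. Person-years are the summed duration divided by 365.25. Treatment-emergent AEs are collected up to 30 days after last dose, and the vital-sign, Skindex-16 and MDASI tables apply a 30-day exclusion after it. The 24- and 52-week disposition tables keep patients with a duration of at most 168 and 364 days.

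**The concern.** A bottle's return date shows when the patient came to the clinic, not when the last capsule was swallowed. The two agree if the patient stops on the day of the visit. If the patient stops earlier, the rule gets back to the true date only when the diary shows missed doses in one unbroken group running through the return date. The diary is for missed doses, and neither document asks a patient who has permanently stopped to keep logging days until the bottle is handed over. The SAP's Exposure section itself expects that visits may be delayed.

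Exposure to study medication is a primary variable in Protocol 8.1.1. An undocumented gap would count as treatment time and, through the days-minus-capsules formula, as non-adherence while still on treatment. It would also shift the windows that decide which AEs and assessments enter the tables.

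**Working it through.** **1. Reproduce the SAP's example.** SAP, Exposure, Programming Note: first dose 1 January, last dose 28 February, 55 capsules taken.

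- Duration = last − first + 1 = 31 + 28 = 59 days.
- Missed doses = 59 − 55 = 4, as the SAP states. An exclusive count would give 58 − 55 = 3, so the days must be counted inclusively.

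**2. Add a lag.** Suppose the last capsule is still taken on 28 February, but the bottle returns L days later and the diary has no entries after the stop. L is an assumption, since the documents give no figure. Under the SAP rule:

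| L (days) | Duration, 59 + L | Missed doses, 59 + L − 55 | Person-years, (59 + L)/365.25 | AE window ends, days after true stop, 30 + L |
|---|---|---|---|---|
| 0 | 59 | 4 | 0.1615 | 30 |
| 7 | 66 | 11 | 0.1807 | 37 |
| 14 | 73 | 18 | 0.1999 | 44 |
| 28 | 87 | 32 | 0.2382 | 58 |

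The first row holds at every L in two cases: if last dose is capped at the true stop date, or if the diary marks every post-stop day through the return date as missed. In the second case the SAP's fallback already gives the right answer.

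**3. What does not move.** Cumulative dose is capsules taken × 150 mg = 55 × 150 = 8,250 mg at every L. Dose intensity is capsules taken over capsules dispensed and contains no dates.

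**4. Cut-points.** Protocol Table 1 puts Cycle 7 Day 1 at Day 169. A patient who stops during Cycle 6 and returns the bottle at that visit, with no post-stop entries, gets a duration of 169 days. Since 169 > 168, the patient drops out of the 24-week table. Likewise Cycle 14 Day 1 is Day 1 + 13 × 28 = 365, which exceeds the 364-day limit of the 52-week table.

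**5. Scale over the study.** Extra person-years = N × share affected × L / 365.25. The SAP's Summary of Deaths shows N = 1215. If half were affected, L = 7, 14 or 28 gives 11.6, 23.3 or 46.6 extra person-years. If all were affected, it gives 23.3, 46.6 or 93.1. The shares are assumptions, and the second set is a ceiling, because patients still on treatment at the cut-off have no post-stop lag.

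**The case against.** The strongest reply is that the plan already has two safeguards. The fallback in the same sentence corrects the date whenever the diary covers the gap. The SAP has patients record doses missed for any reason, and the protocol has them bring the diary to each visit so that the investigator can enter missed doses. The End of Treatment Visit, with drug accountability, is due at discontinuation, so a long lag would go against the schedule. The listing that shows both dates also makes discrepancies visible. All of this stands. It makes the error conditional and limits the lag, but it does not close the gap, because neither safeguard works when the visit is late and the diary is silent. A listing changes no derived value.

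A second reply is that the proposed cap is unproven, because nothing says the discontinuation date is the date of the last capsule. If it is the visit date, the cap does nothing. If it is a decision date before the last capsule, the cap would remove real exposure. This also stands, and the fix needs a guard.

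A reader might infer more than the documents support:

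- **That exposure is overstated as a matter of course.** It is not where drug is returned on the last-capsule day or the diary is complete.
- **That AE rates per 100 patient-years are understated.** The SAP does not define that table's denominator, and a longer treatment-emergent window can add events to the numerator. The net direction is not established.
- **That patients stopping for toxicity are hit hardest.** Nothing in either document shows this.
- **That a percentage inflation can be worked out from 9.7 months.** That figure is the median duration of therapy in the locally advanced cohort of the earlier pivotal trial, not a mean for this study.

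**Conclusion.** The point holds as a conditional gap in the derivation. Applied as written, the rule turns any undocumented interval between stopping and returning drug into treatment duration, person-time, missed doses and longer 30-day windows, one for one in days, and it can move patients across the 24- and 52-week limits. Capsule-based exposure measures are sound.

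The effect per affected patient is exact once a lag is assumed. The study-level effect cannot be established, since it rests on three quantities that the documents do not give: the lag, the share of patients who stop before the return visit, and diary completeness. It may be nil. This is a minor, inexpensive improvement and does not call the exposure tables into question as a whole.

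**What to change.** Define last dose as the earlier of the currently derived date and the treatment-discontinuation date on the End of Study Treatment page, and never later than the date of death. State in the SAP what the CRF discontinuation date represents.

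Add one guard: if the capped date leaves fewer days than capsules recorded as taken, keep the derived date and query the record. In the SAP's example, a discontinuation date of 20 February would leave 31 + 20 = 51 days for 55 capsules, so the cap would be refused. The guard is partial. A date of 26 February leaves 57 days, passes the check and loses two real days. It therefore catches only cuts larger than the number of genuinely missed doses.

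Report the number of patients and days changed by the cap. If few change, the current exposure tables are confirmed. The cost is about one line of derivation, the guard and a few records to query. There is little or no gain where the discontinuation date is simply the visit date.
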